5.8 DOSE MODIFICATION AND DISCONTINUATION

The following symptoms and laboratory abnormalities measured at a single occasion or repeatedly, are considered to be the main guide for the decision about dose modification or treatment interruption:

- Growth factors plasma levels:
 - **Repeated consecutive IGF-I > +2.0 SDS**
- Glucose tolerance
 - HbA1c level > 6.2 %
 - Fasting glucose level is > 5.5 mmol/L
- Increase of liver enzymes ($\geq 2x$ of ULN)
- Immune response
 - Development of high anti-growth hormone antibody titre with strong neutralizing effect
- Any other CTC grade 3 or 4 laboratory abnormality
- Development of intracranial hypertension or pseudotumor cerebri - If a patient has persistent severe headaches for more than 1 day not relieved by aspirin or other analgesics or visual disturbances, then examine the patient for papilledema (to be confirmed by an ophthalmologist). If there is papilledema, perform an MRI of the head with contrast; if there are signs of intracranial hypertension, perform a lumbar puncture (LP) and record the opening pressure. Only positive MRI findings and increased opening pressure on LP confirm the diagnosis of pseudotumor.

In the Main Study, dose efficacy will be analysed first after 6 months of treatment on an individual patient level. Patients who do not achieve the minimally satisfactory growth rate (i.e. delta height SDS of at least 0.2) at this time point will be moved to the next highest dose group for the remaining 6 months of treatment. Dose efficacy will be analysed again after 12 months of treatment on an individual patient level. Patients who do not achieve the minimally satisfactory growth rate at this time point will be moved to the next highest dose group. If the patient is in the highest dose group, the Coordinating Investigator of the study will be informed.

OPKO Biologics	Protocol for Clinical Study CP-4-004	Page 73 of 133
Effective Date: Date of final electronic approval		

Cohort 1-3 patients transitioning to the OLE will continue with the same dose (mg/kg) in which they completed the main study.

In the OLE period, the patients who were in cohort 4, in the main study (e.g. treated with Genotropin) will be randomized to one of the MOD-4023 treatment groups.

In the LT-OLE period, all patients will be switched to the highest MOD-4023 dose 0.66 mg/kg/week.

In the LT-OLE-PEN period, patients should continue with the same dose.

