9.6 Laboratory Test Results

Clinical laboratory measurements will be summarized with descriptive statistics at each visit. Changes within each 12 month period will use the first visit of the 12 month period as the baseline. For Period V the baseline will be the first visit with PEN injection. If data from the first visit of each period are not available, the last previous visit data will be used. Summary of abnormal results (reported as low, high, clinically significant) will be provided for each 12 month period, with the number of patients at the beginning of each period for the denominator.

The following laboratory results will be presented:

Glucose Metabolism	Endocrinology	Lipid Metabolism
Fasting blood Glucose	FT4	Cholesterol
Fasting Insulin	Т3	High density lipoprotein (HDL)
HbA1c	Thyrotropin (= TSH)	Low density lipoprotein (LDL) Cholesterol
	Cortisol, Free	Lipoprotein-A
	Females >=12 y.o.: FSH, LH and estradiol	Triglycerides
	Male >=13 y.o.: FSH, LH and testosterone	

Glucose Metabolism, Endocrinology, and Lipid Metabolism:

Clinical Chemistry	Hematology	Urinalysis
Albumin	Differential Blood Count of Leukocytes	Bilirubin
Alkaline phosphatase	Erythrocyte Count	Glucose
Calcium	Hematocrit	Ketones
Chloride	Hemoglobin	Leukocyte Esterase
Creatinine	Leukocytes	Nitrite
Gamma-glutamyl Transferase (GGT)	Mean Corpuscular Hemoglobin (MCH)	рН
Lactate Dehydrogenase (LDH)	Mean Corpuscular Hemoglobin Concentration (MCHC)	Protein
Phosphate	Mean Corpuscular Volume (MCV)	Specific Gravity
Potassium	Platelet Count	Urinalysis Blood
Serum Glutamic Oxaloacetic Transaminase (SGOT)		Urobilinogen
Serum Glutamic Pyruvic Transaminase (SGPT)		
Serum Iron and Transferrin		
Sodium		
Total Bilirubin		
Total Proteins		
Urea (blood urea nitrogen)		
Uric Acid		

• Chemistry, Hematology, and Urinalysis:

The increases in alanine aminotransferase (ALT), aspartate aminotransferase (AST), and total bilirubin will be examined for liver function. The count and percentage of the increases will be tabulated for each visit including baseline. The increases of ALT and AST will be examined in three categories, i.e. $>2 \times$ upper limit of normal (ULN), $>3 \times$ ULN, and $>5 \times$ ULN, and that of total bilirubin combined with ALT or AST increases will be examined in 1 category, total bilirubin $>3 \times$ ULN and ALT or AST $>2 \times$ ULN.

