14.5.5.2	Laboratory Test Abnormal Results – Hematology: Full Analysis Set
14.5.6.1	Laboratory Test Results – Urinalysis: Full Analysis Set
14.5.6.2	Laboratory Test Abnormal Results – Urinalysis: Full Analysis Set
14.5.7	Laboratory Test Results – Increases in ALT, AST, and Total Bilirubin: Full Analysis Set
14.6.1	Vital Signs by Visit and Change from Start of OLE: Full Analysis Set
14.6.2	Physical Examination Abnormalities by Visit: Full Analysis Set
14.6.3.1	ECG Results by Visit and Change Within Each Year: Full Analysis Set
14.6.3.2	Electrocardiogram (ECG) Abnormal Shifts by Year: Full Analysis Set
14.6.4	Concomitant Medications Within Each Year by ATC2 and Preferred Term: Full Analysis Set
14.7.1	Total Duration of Treatment: Full Analysis Set
3.1.1	Summary of treatment emergent adverse event (All causality) by SOC and PT (Safety Analysis Set)
6.1.1	Summary of treatment-emergent adverse events leading to study drug withdrawn (All Causalities) (Safety Analysis Set)
6.1.2	Summary of treatment-emergent adverse events leading to study drug reduction or interruption (All Causalities) (Safety Analysis Set)
6.1.3	Summary of treatment-emergent adverse events leading to study discontinuation (All Causalities) (Safety Analysis Set)
OC15.4	Annual Incidence and Severity of Treatment-Emergent Adverse Events by SOC and Preferred Term: Full Analysis Set
OC15.6	Annual Incidence and Relationship of Treatment-Emergent Adverse Events by SOC and Preferred Term: Full Analysis Set

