11.3 Figures

Figure No.	Description
7	Height SDS and Cumulative Change in Height SDS by Year and by ADA Status in Study (All Cohorts Combined)
8	IGF-1 SDS by Year by ADA Status in Study
14.2.1.1&2	Annualized Height Velocity
14.2.1.3	Summary of Annualized Height Velocity for All Cohorts Combined at Each Year of Study
14.2.2.2A	Summary of Height SDS by Initial Cohort Assignment at Each Year of Study
14.2.2.2B	Summary of Height SDS by Year of Study and Initial Cohort Assignment
14.2.2.2C	Summary of Height SDS for All Cohorts Combined at Each Year of Study
14.3.5.1	IGF-1 SDS
14.4.2.1&2	Annualized Height Velocity by ADA Status
14.4.2.3	Summary of Annualized Height Velocity for All Cohorts Combined at Each Year of Study by ADA Status
14.4.2.5&8	Summary of Height SDS for All Cohorts Combined at Each Year of Study by ADA Status
14.4.2.9	Peak IGF-1 SDS by ADA Status
14.5.1.1	Clinical Laboratory Summary: Glucose Metabolism
14.5.2.1	Clinical Laboratory Summary: Endocrinology

Figure No.	Description
14.5.3.1	Clinical Laboratory Summary: Lipid Profile
14.5.4.1	Clinical Laboratory Summary: Chemistry
14.5.5.1	Clinical Laboratory Summary: Hematology
14.5.6.1	Clinical Laboratory Summary: Urinalysis
16.2.8.7	Maximum Bilirubin Versus Maximum ALT and AST

Signature Page for CP-4-004 OLE SAP v6.0

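### The SAP's only joint liver category needs bilirubin above 3×ULN, so marked ALT/AST rises with lower bilirubin are never counted as a joint event in Table 14.5.7

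*SAP*

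**What the plan says.** SAP 9.6 plans a liver-function tabulation from ALT, AST and total bilirubin. For the enzymes, "The increases of ALT and AST will be examined in three categories": >2×, >3× and >5×ULN. For bilirubin there is no category of its own; "that of total bilirubin combined with ALT or AST increases will be examined in 1 category", defined as "total bilirubin $>3 \times$ ULN and ALT or AST $>2 \times$ ULN". On the unit of counting, "The count and percentage of the increases will be tabulated for each visit including baseline". The SAP gives no reason for choosing this pair of multiples.

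The output is Table 14.5.7 (SAP 11.1), "Laboratory Test Results – Increases in ALT, AST, and Total Bilirubin: Full Analysis Set". The only other output that joins the analytes is Figure 16.2.8.7 (SAP 11.3), "Maximum Bilirubin Versus Maximum ALT and AST". It has no stated thresholds and no count.

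Two general rules govern what reaches a by-visit table. Under SAP 7.4, unscheduled assessments are listed but left out of visit summaries. Under SAP 7.5, when a visit has more than one evaluable laboratory result, the latest one is used.

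**The concern.** SAP 3.1.1 makes safety the primary objective of this analysis, and Table 14.5.7 holds the only tabulated count of enzyme and bilirubin elevation together. That count sets aside the two upper enzyme grades that the same paragraph has just defined. It cannot tell a marked enzyme rise from a minimal one, and it does not respond to any bilirubin value up to 3×ULN.

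Counting by visit narrows it further. A patient whose enzymes peak at one visit and whose bilirubin peaks at another need not qualify at either. Protocol 5.5.1 uses unscheduled visits to follow up abnormal or alarming laboratory values, and those results do not reach the row. A repeat within a visit that has come down replaces the peak.

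At stake is how a zero in the row is read. A reader of the study report could take it to mean that no child had a marked enzyme rise together with raised bilirubin. The row does not establish that.

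**Working it through.** No sample size, power or error rate enters this point, and the plan has no figure to reproduce. The check applies the rule in SAP 9.6 to pairs of values.

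Inputs, all in multiples of ULN:
- E = the higher of ALT and AST; B = total bilirubin.
- Enzyme-only rows (SAP 9.6): E >2, E >3, E >5.
- Joint row (SAP 9.6): B >3 and E >2.
- Comparison row (an assumption; neither document gives it): B >2 and E >3.

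| E | B | Enzyme-only rows entered | SAP joint row | Comparison row |
|---|---|---|---|---|
| 3.5 | 2.5 | >2, >3 | no | yes |
| 6 | 2.5 | >2, >3, >5 | no | yes |
| 6 | 2.9 | >2, >3, >5 | no | yes |
| 10 | 2.1 | >2, >3, >5 | no | yes |
| 10 | 2.9 | >2, >3, >5 | no | yes |
| 2.1 | 3.1 | >2 | yes | no |
| 2.5 | 3.5 | >2 | yes | no |
| 10 | 3.1 | >2, >3, >5 | yes | yes |

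Three things follow.

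1. The SAP joint row requires B >3. For B ≤3 it is empty at every value of E, so five of the eight pairs fail it, four of them with E in the SAP's top enzyme grade.
2. The comparison row picks up those five but loses 2.1/3.1 and 2.5/3.5, which the SAP row catches. Replacing one row by the other exchanges one blind area for another. Keeping both captures all eight pairs.
3. By-visit counting is a separate restriction. Suppose E >2 with B ≤3 at one visit, and B >3 with E ≤2 at another. Neither visit satisfies the rule, although the patient's maxima over the period do.

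Scale: SAP 4.1 gives 53 patients starting the extension. One patient is 1/53 = 1.9%. The documents give no expected rate of such events, and later visits may have fewer patients, so this shows only what one case would be worth.

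Other places where a joint event might be counted:
- The 17 adverse events of special interest in SAP 9.1 include no hepatic category.
- Under Protocol 7.1 a laboratory abnormality is an adverse event only if it causes signs or symptoms, is judged clinically significant or needs therapy.
- The abnormal-results summary in SAP 9.6 (Table 14.5.4.2 for chemistry) works by low, high and clinically significant. It uses no multiples of ULN and does not join analytes.

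**The case against.** The strongest reply is that nothing is lost from view. A child with ALT 6×ULN and bilirubin 2.9×ULN enters all three enzyme rows, falls within the abnormal-results summary, appears in Listing 16.2.8.7 and is plotted in Figure 16.2.8.7. With 53 patients, outlying points on that figure can be read one by one, and the figure already uses maxima. In Period IV routine chemistry is scheduled about once a year, apart from a visit three months after the dose switch for some patients, so scheduled by-visit and by-year counts nearly coincide there. The analysis is descriptive, with no hypothesis tests (SAP 7.1).

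Most of this stands. A reader might infer that marked enzyme rises would go unreported; the outputs just listed show otherwise. It does not close the gap, because the enzyme rows ignore bilirubin, and the figure carries no thresholds or count and may pair maxima from different visits.

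A reader might also infer that the two multiples were transposed by mistake. The documents do not support that. Neither cites an external liver screen, and Protocol 5.8 itself lists enzymes at or above 2×ULN among the findings that guide dose decisions, so a 2× enzyme cut is not evidently a slip. The SAP does not say that this is its reason, but the point has to rest on what the row can and cannot count.

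**Conclusion.** The point holds as a limited gap in reporting. The single joint row in SAP 9.6 cannot count any enzyme rise, including one above 5×ULN, when bilirubin is at or below 3×ULN. By-visit counting, the exclusion of unscheduled results and the latest-result rule narrow it further. The thresholds are read directly from the SAP, and this conclusion needs no outside benchmark.

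The consequence is modest. No test, interval or error rate changes, and the values remain visible elsewhere. The figure of 1 in 53 is illustrative and predicts no event. The particular cuts proposed for an added row are an assumption, and another pairing with a higher enzyme cut and a lower bilirubin cut would serve. This is an inexpensive improvement to a safety table and does not invalidate the analysis.

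**What to change.** In SAP 9.6 and Table 14.5.7:

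- Keep the existing joint row and add a second. Proposed, as an assumption: ALT or AST >3×ULN with total bilirubin >2×ULN. Do not substitute it for the existing row, for the reason shown in the working.
- For both joint rows, count each patient once per 12-month period, and once for Period V, if any result in the interval qualifies. SAP 9.4 already does this within each 12-month period for IGF-1 SDS >2, and SAP 9.1 already treats Period V cumulatively for adverse events. State the denominator.
- Include unscheduled and repeat results, as an explicit exception to SAP 7.4 and 7.5. Protocol 5.5.1 allows local laboratories at unscheduled visits, so take each multiple against the ULN of the laboratory that ran the sample.
- If per-patient maxima are used, flag whether the two elevations were concurrent.
- Draw the same reference lines on Figure 16.2.8.7.

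The cost is one table row, some programming for the period-level count, and reference lines on an existing figure. No new data are collected and no clinical rule changes. The drawback is that per-patient maxima can join peaks from different dates, which is why the concurrence flag is needed. If the sponsor prefers the present pairing alone, the SAP should give the reason and state that the row does not respond to bilirubin at or below 3×ULN.

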9.7 Physical Examinations

Physical examination data (every three months in Period III and every 12 months in the later period) will be tabulated by frequency count and percentage for each organ system category by visit.

9.8 Vital Signs

The vital signs (systolic / diastolic blood pressure in seated position, respiratory rate, pulse rate, and body temperature) will be summarized at each visit. The change from the beginning of OLE, and the change within each year for continuous parameters will be presented.

9.9 ECG

The ECG parameters (heart rate, PR interval, QRS interval, QT interval, RR intervals, QTc-_{Bazett} interval) will be listed. The clinical assessments: Normal / Abnormal – same as screening / Abnormal – new, clinically not significant / Abnormal – new, clinically significant or aggravated, collected at the end of each OLE and PEN year will be summarized as proportion of patients with each assessment, with the number of patients at the beginning of the period as the denominator.

9.10 Magnetic Resonance Imaging (MRI)

MRI results will be listed for each visit.

9.11 Fundoscopy

The fundoscopy examination is done at the end of the first year of the OLE period and performed if there is any clinical sign of intracranial hypertension. The number and percentage of patients who have fundoscopy done in each 12 month period, and the number and percentage of patients who have signs of intracranial hypertension in each period will be presented.

9.12 Concomitant Medications

Medications will be coded and presented using World Health Organization (WHO) Drug Dictionary version September 2017, Anatomical Therapeutic Chemical Code (ATC) level 2, as well as, the primary term. The medications used within each 12 month period will be summarized by ATC level 2. For PEN treatment in Period V, the medications will be separately summarized.

9.13 Extent of Exposure

The total duration of treatment (in months) for each patient will be calculated as:

- 1. The total duration since first treatment in this study (since the first dose of Period I)
 - a. For patients initially randomized to Genotropin, the total duration of exposure to somatrogon will be calculated from the date for first treatment with somatrogon.
- 2. The total duration in each assigned dose level and on PEN.
- 3. The overall exposure will be calculated as Last dose First dose + 7 days (to account for the once weekly dose exposure). To convert to months, the total daily exposure will be divided by 30.147.

Because of potential gaps in treatment between periods, the total duration may not represent continuous exposure. A listing of the patients with gaps in treatment will be provided showing the time period without treatment.

The number and proportion of patients who have the dose adjusted due to IGF-1 SDS >2 or other reasons will be summarized by reason for each 12 month period, with the denominator as the number of patients who started each period. The listings will show the dose at which the IGF-1 SDS excursion occurred.

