9 ANALYSIS OF SAFETY ENDPOINTS

9.1 Adverse Events

AEs will be coded using MedDRA v20.1. TEAEs for each 12 month period will be defined as those that start in each 12 month period and separately for Period V on PEN, which will be cumulative. The denominator used for calculation of AE rates will be the number of patients at the beginning of each period or year. For patients who have gaps in treatment, the events that start in the gap will be included in the prior treatment period. In addition, a summary of AEs for the entire extension period will be provided.

The results will be presented:

- by order of the frequency of AEs by the MedDRA preferred term (PT)
- by severity of AEs
- by the relationship of AEs to the study drug
- and all SAEs

Patient incidence of AEs of special interest will also be summarized overall and by SOC through the entire extension period. The AEs of special interest are:

Adverse Event of Special Interest	MedDRA v20.1 Definition Criteria
Glucose metabolism impairment	Hyperglycaemia/new onset diabetes mellitus (standardized medDRA queries [SMQ]) Full Scope
Thyroid function impairment	Thyroid dysfunction (SMQ) Full Scope
Intracranial hypertension	Increased intracranial pressure disorders (high level term [HLT] - All Paths)
Neoplasias	Malignancy (SMQ) Full Scope
Intracranial aneurysm	Central nervous system aneurysms and dissections (HLT - All Paths)
Immunogenicity (including positive anti-drug antibody and allergic reactions) and Hypersensitivity	Laboratory result parameter: Anti somatrogon antibody or Neutralizing Antibody present, Anaphylactic reaction (SMQ) Narrow Scope, Angioedema (SMQ) Narrow Scope, Hypersensitivity (SMQ) Narrow Scope
Injection site reactions (including lipoatrophy/skin dystrophy)	Injection site reactions (HLT - All Paths) and select PTs (Lack of injection site rotation, Lipoatrophy, Skin hypertrophy, and Skin dystrophy) and PTs containing 'Administration site'
Epiphysiolysis	PT Epiphysiolysis
Haemangioma of skin	PT Haemangioma of skin
Oedema	Oedema NEC (HLT - All paths) and Total fluid volume increased (HLT - All Paths)
Scoliosis	PT Scoliosis
Acute and chronic pancreatitis	Acute and chronic pancreatitis (HLT - All Paths)
Increased Protein kinase	PT Blood creatine phosphokinase increased

Adverse Event of Special Interest	MedDRA v20.1 Definition Criteria
Adrenal cortical hypofunctions	Adrenal cortical hypofunctions (HLT - All Paths)
Myalgia	PT of Myalgia
Myositis	PT of Myositis
Arthralgia	PT of Arthralgia

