10 GROWTH OUTCOMES

10.1 Annualized HV

Descriptive statistics or HT will be presented. Annualized HV between two time intervals X and Y will be calculated as:

$$\begin{aligned} \text{Height Velocity} & \left(\frac{cm}{year}\right) \\ &= \left[\frac{\text{Month X Height (cm)} - \text{Reference Month Y Height (cm)}}{\text{Month X date} - \text{Reference Month Y date}}\right] * 365.25 \end{aligned}$$

HV will be calculated for the following intervals:

- 1. Periods III and IV
 - a. 12 month intervals, with the first 12 months starting with the first injection of Period III. Gaps in treatment will not alter that calculation of these 12 month intervals.
 - b. Last 6 and 12 month interval, using the last measure in Period IV with the measures at 6 and 12 months prior to the last measure as the reference.
- 2. Period V (PEN)
 - a. Intervals of 6 and 12 months from the start of the PEN injection as the reference for the first year.
 - b. After the first year of PEN, HV at the end of each year uses the measure at the Month 12 visit in each year with the measure at the Month 12 visit of the prior year as the reference. In cases where there is a gap in treatment between years, the measure at the restart of treatment (if available) will be used as the reference.

HV will also be presented for each treatment year, including Periods I and II, by the original treatment group assignment.

For patients who discontinue from the study between these specific defined visits for the calculations, their last HT measurement and date will be used for the annualized HV in the interval of interest.

Annualized HV by year, annualized HV on PEN treatment, change in HT SDS by year and change in HT SDS on PEN treatment will be summarized by ADA status.

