10.3 Change in Height SDS

HT SDS will be summarized with descriptive statistics at the end of OLE years 1 - 4 and for each year on PEN. HT SDS will also be presented for each treatment year, including Period I and II, by the original treatment group assignment and total. In addition, HT SDS will be summarized by ADA status. Descriptive statistics will be used to characterize the change in HT SDS. The change in HT SDS will be calculated from baseline of Period I, as well as each 12 month period.

In addition, the cumulative change in HT SDS from the baseline at Period I will be calculated for each of the scheduled Month 12 visit of each year, using the original treatment groups assignment and total.

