10.4 Bone Maturation

BM will be evaluated as the BA divided by the chronological age (CA).

BM = BA/CA

BA is reported as year and months, and will be converted to a decimal value as years + months/12.

CA will be calculated as (date of BA assessment – Birth date)/365.25.

BM will be calculated at 12 month intervals. The change in BM will be calculated as the change in BA/change in CA for each of the intervals defined for the calculation of HV, when the BA assessment is available. Descriptive statistics will be used to characterize the change in BM.

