11.2 Listings

Listing No.	Description
16.1.7	Randomization
16.2.1.1	Patient Disposition
16.2.1.1b	Patient Disposition - CP-4-004 OLE
16.2.1.1c	Listing of Patients final height as of last known visit in Study CP-4-004
16.2.1.2	Trial Inclusion/Exclusion Criteria
16.2.1.3	Inclusion/Exclusion Criteria Not Met
16.2.10	Comments
16.2.2	Protocol Deviations
16.2.4.1	Patient Demographics
16.2.4.2	Medical History at Start of Main Study
16.2.4.3	ACTH Test Results
16.2.4.4	MRI Results
16.2.4.5	Pubertal Status at Start of OLE (Year 1)
16.2.5.1	Patient Visits
16.2.5.2	Drug Accountability
16.2.6.1	Height, Height SDS, Change in Height SDS, and Height Velocity at Each Visit
16.2.6.1.b	Listing of antibodies and efficacy data in all patients in Study CP-4-004 OLE
16.2.6.2	Bone Age by Visit
16.2.6.3	Bone Maturation by Visit
16.2.7.1	All Adverse Events
16.2.7.2	All Serious Adverse Events
16.2.7.3	All Adverse Events Leading to Withdrawal from the Study
16.2.7.4	All Adverse Events of Special Interest
16.2.7.5	All Injection Site Reactions
16.2.8.1	IGF-1 and IGF-1 SDS Results at Each Visit
16.2.8.2	IGF-1 SDS > 2
16.2.8.3	IGFBP-3 Results at Each Visit
16.2.8.4	Glucose Metabolism Results
16.2.8.5	Endocrinology Results
16.2.8.6	Lipid Metabolism Results
16.2.8.7	Chemistry Results
16.2.8.8	Hematology Results
16.2.8.9	Urinalysis Results

Listing No.	Description
16.2.8.10	Pregnancy Test Results
16.2.8.11	Gonadotropic Hormone Results
16.2.8.12	MOD-4023 Serum Levels
16.2.9.1	Vital Sign Results by Visit
16.2.9.2	Physical Examination Results
16.2.9.3	Electrocardiogram Results
16.2.9.4	Concomitant Medications
16.2.9.5	Exposure and Duration of Treatment
16.2.9.6	Antibody Titers
16.2.9.6b	Antibody Titers (Anti-hGH Nab)
16.2.9.7	Injection Site Pain, Redness, Bruising, Swelling, and Itching Scores by Visit
16.2.9.8	Fundoscopy
16.2.9.9	Weight and Height at Each Visit
16.2.9.10	Pubertal Status by Visit
16.2.9.11	Summary of Dose Adjustments
16.2.9.12	Listing of antibodies to somatrogon and individual efficacy data in patients with CTP+ in Study CP-4-004 (Main and OLE)

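### SAP 9.13 divides exposure days by 30.147 to get months; this is no month length and, as written, overstates exposure by about 0.9 to 1.0%

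*SAP*

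**What the plan says.** SAP 9.13 opens with "The total duration of treatment (in months) for each patient will be calculated as" and then lists three items:

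1. Duration since first treatment in the study, with a separate somatrogon duration for patients who began on Genotropin.
2. Duration at each assigned dose level and on PEN.
3. Overall exposure, taken as last dose minus first dose plus 7 days (the minus sign is missing from the text as read, which I treat as a reading artefact). This item contains the conversion: "To convert to months, the total daily exposure will be divided by 30.147".

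The SAP gives no source for 30.147, and the number appears nowhere else in either document.

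Two other sections fix a year length. In 10.1, under "Annualized HV between two time intervals X and Y will be calculated as", the height difference over the date difference is multiplied by 365.25. In 10.4, chronological age ends in "Birth date)/365.25", and bone age is converted with 12 months to the year.

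The outputs concerned are Table 14.7.1, "Total Duration of Treatment: Full Analysis Set", and Listing 16.2.9.5, "Exposure and Duration of Treatment".

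**The concern.** A days-to-months divisor should be one twelfth of a year, and 30.147 is not. It also disagrees with the year length the SAP uses elsewhere, so the same interval would be exactly one year for height velocity and age but more than 12 months for exposure.

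The primary objective of this analysis is safety in extended treatment, and duration of exposure is the background against which those data are read. The error always lengthens exposure and grows in absolute terms with follow-up. Anyone recomputing months from the dose dates with a standard month would not reproduce the listing.

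**Working it through.** **Inputs**

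- Divisor: 30.147 days per month (SAP 9.13).
- Year length: 365.25 days (SAP 10.1 and 10.4).
- Months per year: 12 (SAP 10.4, bone age).
- Alternative year of 365 days: my assumption, included because 365/12 rounds to 30.417, which is 30.147 with the 1 and 4 exchanged.

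**Can 30.147 be reproduced?**

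12 × 30.147 = 361.764 days. That is 3.49 days short of 365.25 and 3.24 days short of 365 (differences rounded). The candidate month lengths are:

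| Basis | Days per month | Months overstated by (basis / 30.147 − 1) |
|---|---|---|
| 365.25/12 | 30.4375 | 0.964% |
| 365.2425/12 | 30.4369 | 0.962% |
| 365/12 | 30.4167 | 0.895% |
| 366/12 | 30.5 | 1.171% |
| 364/12 | 30.3333 | 0.618% |
| 30-day month | 30 | −0.488% |

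The roundings 30.4, 30.42 and 30.44 and whole months of 28, 29 and 31 days do not give 30.147 either. Nothing in the SAP supports a 30-day month.

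**Size on the SAP's own 365.25-day year**

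Reported months = days / 30.147. Excess in days = excess months × 30.4375.

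| Days | True months | Reported months | Excess (months) | Excess (days) |
|---|---|---|---|---|
| 365.25 | 12 | 12.116 | 0.116 | 3.5 |
| 730.5 | 24 | 24.231 | 0.231 | 7.0 |
| 1461 | 48 | 48.463 | 0.463 | 14.1 |
| 1826.25 | 60 | 60.578 | 0.578 | 17.6 |

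**Size on a 365-day year**

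365 / 30.147 = 12.107 months (3.3 days too long), 730 / 30.147 = 24.215 (6.5 days) and 1825 / 30.147 = 60.537 (16.3 days).

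**When the excess reaches 0.1 month**

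0.1 / 0.009636 = 10.4 months of exposure, or 0.1 / 0.008945 = 11.2 months on the 365/12 basis.

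The durations are illustrative, since the documents give no actual exposure. The 60-month row is the main-study year plus four extension years (12 + 48), a span taken from SAP 10.3, which summarises height SDS "at the end of OLE years 1 - 4 and for each year on PEN". For a patient who started on Genotropin, the same calendar gives 48 months of somatrogon.

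**What does not change**

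SAP 9.1 states: "The denominator used for calculation of AE rates will be the number of patients at the beginning of each period or year". Adverse event rates therefore do not use exposure time. Height velocity and chronological age use 365.25 directly. SAP 7.1 plans no formal hypothesis testing.

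**The case against.** The strongest reply is that this cannot alter any conclusion. The factor is constant across patients and groups and touches only a descriptive summary. That is right, and it is why the point is minor.

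The measure is also already approximate. SAP 9.13 warns that gaps between periods may make total duration differ from continuous exposure, and footnote 1 of protocol Appendix 3 provides for patients off treatment for more than 60 days before the long-term extension. One such gap adds about 60/30.4375 = 2.0 months, more than three times the 0.58 month that the divisor adds at five years. That puts the size in proportion. But gaps are disclosed and listed, whereas the divisor error is not visible to the reader.

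Three further limits stand:

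- The overstatement is conditional. If the analysis program uses a correct constant, only the SAP text is wrong. The programs are not available to check.
- The divisor is written only into item 3. Its extension to items 1 and 2 is inferred from the lead-in, which puts all durations in months, and from the absence of any other divisor. The table and listing titles give no unit.
- The 0.1-month threshold matters only if results are shown to one decimal, and the SAP states no reporting precision.

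A reading error in the PDF text cannot be wholly excluded, since the minus sign in the same item is missing. An exchange of two digits is not a typical reading error, however, and a look at the source file would settle it. None of this makes 30.147 a valid month.

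**Conclusion.** The divisor is wrong as written. Applied literally, it overstates overall exposure in months by 0.96% on the SAP's 365.25-day year, or 0.89% on a 365-day year. By the lead-in, the same apparently holds for every duration in Table 14.7.1 and Listing 16.2.9.5.

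The finding assumes that an average calendar month was intended and that the programs follow the text. A mistyped 30.417 is plausible but is inference. Severity is minor: the listed and tabulated exposure values would be incorrect, but no safety rate, growth result or between-group contrast would be distorted.

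**What to change.** In SAP 9.13, replace 30.147 with 30.4375 (365.25/12), in line with 10.1 and 10.4, and add a clause saying that the same divisor applies to items 1 and 2. Using 30.417 would also remove the error, and the two differ by only about 0.07% (30.4375/30.417 − 1), but it would leave two year lengths in one SAP.

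Check the constant in the program for Table 14.7.1 and Listing 16.2.9.5 and align it with the text. If the program already uses a correct value, the SAP text should still be corrected, because SAP section 2 requires differences from the plan to be documented in the study report.

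The cost is one constant and one clause in the SAP and at most one constant in the program. No other planned analysis changes.
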